## **Compensation and/or Reimbursement**

Will compensation or reimbursement for expenses be offered to subjects?

Yes

Please describe and indicate total amount and schedule of payment(s).

Include justification for compensation amounts and indicate if there are bonus payments.

Subjects will receive \$10 for travel at each study visit and will receive an additional \$10 each week for returning their medication bottle with any remaining pills. The maximum amount over the 9 weeks a participant may potentially earn for attending all study visits is \$300 (\$210 (19 study visits during the 8 weeks plus we will ask participants to return for 1 visit in week 9 to gather complete data from week 8 and once in week 10 after titration off of medication is complete) for travel and \$90 for bottle return).

## Uploads

Upload the entire grant application(s)

Upload copy(ies) of unbolted Consent Form(s)

pregab-AUD cf unbolted 5-9-17.pdf

Upload copy(ies) of bolted Consent Form(s)

Upload copy(ies) of the HIPAA form

PP2PDFPrepUEAuthorization 4-18-17.pdf

Upload any additional documents that may be related to this study

7491\_FB\_prov\_app\_memo\_05-10-17.pdf

pregabalin IND exemption.pdf

Study: AN OPEN-LABEL PILOT STUDY OF PREGABALIN AS TREATMENT FOR ALCOHOL USE DISORDERS

PI: [name]

IRB: 7491

NCT#: NCT03256253

Data Analysis Plan created 6-28-2017

Statistical Analyses

Summary statistics of baseline demographics of the sample will be computed using frequencies, means and standard deviations. For skewed distributions, medians and interquartile ranges (IQR) will be computed. Study retention will be summarized using proportions and by computing the mean number of weeks in the trial completed.

For the primary outcome measure, the maximum maintained dose will be reported with mean and standard deviation. For measures of drinking and abstinence for each participant it will be computed during the participant's last week of study participation: proportion of heavy drinking days, proportion of abstinent days, number of drinks per week, and number of drinks per drinking day. The same measures will be computed at baseline using the weekly average over the past 28 days. Wilcoxon signed rank tests will be used to analyze the change from baseline to the last week of study participation. Side effects will be summarized by creating indicators of whether subjects reported: any side effects during the trial, any dose reductions due to side effects, and any discontinuation of medication due to side effects. All analyses will be conducted in SAS® (version 9.4) and all statistical tests were 2-tailed at a significance level of 5%.

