#### Secondary Outcome Measures

- 1) **The proportion of the heavy drinking days** (defined as any day where the number of standard drinks was at least 5 for men and at least 4 for women) per week
- 2) **The percent days abstinent** will be lower at the end of the trial as compared to baseline.
- 3) **Symptoms of alcohol withdrawal** will be reduced as compared to baseline.

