## **Inclusion/Exclusion Criteria**

Name the subject group/sub sample

Adults with AUD

Create or insert table to describe the inclusion criteria and methods to ascertain them

1. Meets DSM-5 criteria for current alcohol use disorder	MINI International Neuropsychiatric Interview for DSM-5; psychiatric evaluation
2. Reports drinking a minimum of 5 standard drinks for men or 4 standard drinks for women at least 4 days per week over the past 28 days	Self-report
3. Between the ages of 18 and 65	Demographics
4. Able to provide informed consent and comply with study procedures	MD assessment

Create or insert table to describe the exclusion criteria and methods to ascertain them

1. Subjects with any current psychiatric disorder as defined by DSM-5, other than AUD, that in the investigator's judgment might require intervention over the course of the study.	MINI International Neuropsychiatric Interview for DSM-5; psychiatric evaluation
2. Subjects receiving psychotropic medication treatment	Medical history; psychiatric evaluation
3. Evidence of moderate-to-severe alcohol withdrawal (CIWA-Ar $\geq 13$ )	Medical evaluation
4. History of alcohol withdrawal seizures or alcohol withdrawal delirium	Medical history
5. History of allergic reaction to candidate medication (pregabalin)	Medical history
6. Pregnancy, lactation, or failure in females patients to use adequate contraceptive methods	Medical history; serum HCG
7. Unstable physical disorders which might make participation hazardous	Medical history; physical examination; ECG; laboratory testing
8. Subjects who have a current DSM-5 diagnosis of moderate or severe substance use disorder, with the exception of alcohol, nicotine and caffeine use disorders. A diagnosis of a mild substance use disorder will not be exclusionary, as long as the current primary substance use disorder is alcohol.	MINI International Neuropsychiatric Interview for DSM-5; psychiatric evaluation; urine toxicology
9. Are legally mandated to participate in alcohol use disorder treatment program	Self-report
10. Cognitively impaired	psychiatric interview; MMSE will be completed on all

individuals over 60  
years old

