### **Research Related Delay to Treatment**

Will research procedures result in a delay to treatment?

Yes

Maximum duration of delay to any treatment

Once screening is completed, there is no delay for study entry for eligible patients.

The patient should receive treatment medication within 2-3 weeks after the initial screening evaluation.

Medical management therapy is an abstinence-focused supportive psychotherapy condition developed for substance use disorder pharmacotherapy clinical trials and will begin in week 1 of the treatment study.

Medical management therapy approximates the level of support of abstinence that patients would expect to receive in community treatment (general support of abstinence, tying improvement to reduction or cessation of drug use, referral to 12-step programs, etc.)

Maximum duration of delay to standard care or treatment of known efficacy

Because the screening procedure sometimes requires 2-3 meetings, individuals may not begin medical management therapy until 2-3 weeks after their initial screening evaluation for the study. Medical management therapy will start during week 1 of the treatment study.

Treatment to be provided at the end of the study

At the conclusion of the 9-week protocol, the participants will be offered supportive therapy for at least one additional month or until an appropriate referral for on-going treatment is made.

If a patient found the medication to be beneficial, they will be given an appropriate referral for ongoing treatment.

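### The SAP's undated 28-day drinking baseline probably overlaps the window used to select heavy drinkers, so regression to the mean biases the change toward a reduction and the 5% level is not assured

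*SAP*

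**What the plan says.** Inclusion criterion 2 (Protocol, Inclusion/Exclusion Criteria) requires a minimum of 5 standard drinks for men or 4 for women "at least 4 days per week over the past 28 days". The secondary outcome counts a heavy drinking day as "any day where the number of standard drinks was at least 5 for men and at least 4 for women" (Protocol, Secondary Outcome Measures). The cut-off for selection and for the outcome is therefore the same.

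For the baseline of the drinking measures the SAP says "The same measures will be computed at baseline using the weekly average over the past 28 days". It does not say on which day those 28 days end. The follow-up value covers one week: "it will be computed during the participant's last week of study participation". The analysis is then: "Wilcoxon signed rank tests will be used to analyze the change from baseline to the last week of study participation", at a two-sided level of 5%.

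On timing, the Protocol says: "The patient should receive treatment medication within 2-3 weeks after the initial screening evaluation" (Research Related Delay to Treatment). The same section adds that eligible patients face no further delay once screening is complete, and attributes the interval to screening that can need 2-3 meetings.

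The trial is open label with one arm. Neither document mentions regression to the mean.

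**The concern.** People are admitted because their recent heavy-day share was high. If the same days serve as baseline, that baseline is cut off from below by the entry rule, while the final week is unrestricted. Some of those admitted were in an unusually heavy spell, and their drinking tends back toward their own average with no help from treatment. In a randomised trial this affects all arms and cancels in the comparison. Here it goes straight into the estimated change.

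At stake is how the drinking results are read. They are secondary, but they carry the only hypothesis tests named in the SAP. A significant fall could be taken as a signal of efficacy when part of it comes from the entry rule.

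**Working it through.** **Inputs from the documents.** Selection: at least 4 heavy days a week over 28 days. Baseline: 28-day average, undated. Follow-up: one week. Test: Wilcoxon signed rank, two-sided 5%. Planned enrolment: 20, with 10 completers required. No control arm.

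**Inputs not in the documents (assumed).** The mean and spread of the heavy-day share among people screened, week-to-week variation within a person, and its autocorrelation. The documents also do not say whether the 4-day rule must be met in every week or on average.

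**Step 1: the floor on baseline.** 4 days × 4 weeks = 16 days, and 16/28 = 57%. On the average reading nobody enters with a baseline heavy-day share below 57% in the selection window. The final week can be anything from 0 to 7 days out of 7.

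**Step 2: the benchmark.** The 5% is a chosen level, so there is no derivation to reproduce. The exact signed-rank distribution gives an attained two-sided size of 0.0484 at n = 20 and 0.0488 at n = 10. Half of 5% lies in the direction of a reduction, so the benchmark is 2.5%. Simulated without selection, a significant reduction appears in about 1-3% of trials. The test itself is sound, and any excess comes from the entry rule.

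**Step 3: error rate with full overlap, no treatment effect, n = 20, rule met on average (16 of 28 days).** Each person has a true heavy-day probability, with random fluctuation added on the logit scale. The rule is applied to the first 28 days, and the 28-day mean is compared with one later week.

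| Screened mean heavy-day share | Chance of a significant reduction |
|---|---|
| 0.5-0.7 | about 4-37% |
| 0.8-0.9 | about 1-6% |

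The rate depends strongly on the assumed fluctuation. A separate run at means of 0.5-0.7 (between-person SD 0.15-0.20) gave:

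| Week and month fluctuation (logit SD) | Fall in heavy-day share | Significant reduction |
|---|---|---|
| none | 1.5-3 points | 4-10% |
| 0.5 | 4-9 points | 8-29% |
| 1.0 | 10-16 points | 19-49% |

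The same model at mean 0.8 (SD 0.15) gave 3.6%, 4.3% and 7.5% for the three fluctuation levels. At mean 0.9 (SD 0.08) it gave 2.0%, 2.5% and 3.6%.

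**Step 4: the every-week reading.** Requiring 4 heavy days in each week selects harder. In a logit-normal model (n = 20, full overlap) the rate exceeded 5% in 16 of 23 scenarios under this reading and in 12 of 22 under the average reading. For near-daily heavy drinkers (enrolled baseline about 93-94%) it stayed at 1.6-4.4% even under the every-week rule.

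**Step 5: partial overlap.** If the SAP window ends at first dose, 2 or 3 weeks after the selection window closes, the shared days are 28 − 14 = 14 or 28 − 21 = 7. In a mid-range example (mean logit 0.85, between-person and weekly SDs both 1, every-week rule, n = 20):

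| Shared days | No autocorrelation | Weekly autocorrelation 0.8 |
|---|---|---|
| 28 | 13% | 28% |
| 14 | 4.5% | 15% |
| 7 | 2.3% | 11% |

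With full overlap and no autocorrelation, the baseline of 84% falls to 78% with no treatment effect. The choice of window date alone moves the error rate several-fold.

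**Step 6: a baseline outside the selection window.** Under the average rule, a two-week baseline after selection brought the rates of Step 3 down to about 1-4%. They still reached 10% with autocorrelation 0.8 and strong fluctuation.

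Only heavy drinking days were simulated. The same direction is expected for abstinent days and drinks per week, but it has not been shown.

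**The case against.** A reader might infer that the two windows are identical and that regression to the mean alone makes a significant reduction more frequent than 5%. The documents support neither. The SAP does not date its window, and a window ending at first dose could share as few as 7 days with the selection window. The size turns on how far participants sit above the threshold, which no document states. If people screened drink heavily about 6 or more days a week, there is little or no inflation. Both points stand, and they limit the claim.

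A reader might also take the 2-3 weeks before medication as a ready-made clean baseline. That interval runs from the initial screening evaluation, and the Protocol says nothing delays entry after screening ends. If criterion 2 is settled at the last meeting, few or no days may remain.

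It can further be said that the SAP tests change from baseline and nowhere claims to isolate a drug effect, that Medical Management and open-label expectancy already prevent attribution, and that the primary outcomes (dose and tolerability) are descriptive. All true. This keeps the point away from the primary results. It does not remove a bias of known direction that the plan leaves unmentioned, or settle a baseline date that can change the result.

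**Conclusion.** The concern holds in limited form. The baseline probably overlaps the selection window and uses the same heavy-day cut-off, so with one arm the expected change in heavy drinking days is biased toward a reduction. The 5% level is not assured as an error rate for no treatment effect.

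Against the 2.5% benchmark, with full overlap, n = 20 and the rule met on average, the chance of a significant reduction is about 4-37% at screened means of 0.5-0.7 and about 1-6% at 0.8-0.9. Stronger fluctuation or an every-week rule raises it, and partial overlap lowers it. All these figures rest on assumed drinking distributions. They do not show that the rate must exceed 5%, nor that an observed fall would be wholly an artefact. The point concerns secondary and exploratory outcomes and should be settled before analysis.

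**What to change.** In the SAP's Statistical Analyses:

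1. Give the start and end dates of the 28-day baseline relative to the window used for inclusion criterion 2.
2. Keep that baseline, and pre-specify a sensitivity analysis using the Timeline Follow-Back days that fall after the inclusion look-back window and before the first dose. Where criterion 2 is assessed at the initial screening evaluation, these days start there.
3. Report the number of such days available per participant, and show both changes side by side with confidence intervals.
4. State that the p-values against zero change include regression to the mean and will not be read as a drug effect.

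The cost is a few SAP sentences and one table. The Timeline Follow-Back is already collected and only needs to be brought up to date on the first dosing day. The limits should be stated too: the second window may be short or absent for some participants, drinking may already fall during screening, and the bias is not fully removed if drinking drifts over several weeks.
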